6.2.5 SENSITIVITY ANALYSES

The primary analysis described in section 6.2.1 uses the joint complete case population for both coprimary outcomes. As a sensitivity analysis we will repeat the analysis using the complete case populations of each of the co-primary outcomes individually (i.e., including participants with valid responses to at least one of the co-primary outcomes) using the same methods as described in section 6.2.1.

A sensitivity analysis will estimate the CACE to account for departures from the randomised intervention. For the purposes of this sensitivity analysis, we will define different analysis populations depending on the level of adherence to the PCT-guided algorithm (Figure 3): TPL/008/2(v1.0) CONFIDENTIAL Page 26 of 38

Canolfan Ymchwil Treialon

Short title:	ISAP / SAP Template

- Patients randomised to PCT-guided care in whom a PCT test is done, and a PCT result is available
- Patients randomised to PCT-guided care in whom a PCT test is done, a PCT result is available, and the clinician has seen the PCT result
- Patients randomised to PCT-guided care in whom a PCT test is done, a PCT result is available, the clinician has seen the PCT result and followed the algorithm exactly.

The non-inferiority margin is defined using a fixed risk difference of 2.5%. If the observed 28-day mortality in the control arm deviates from the 15% (by more than 3% points above or below) assumed in the sample size calculation, we will additionally repeat the primary analysis with the non-inferiority margin modified according to the power-stabilising arcsine transformation proposed by Quartagno et al. (2020 & 2023).

Also, the protocol allows patients to be recruited more than once into the study. If the proportion of repeatedly randomised patients exceeds 5%, we will perform a sensitivity analysis excluding repeat episodes.

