4.2 ADHERENCE AND PROTOCOL DEVIATIONS

4.2.1 DEFINITION AND ASSESSMENT OF ADHERENCE

Adherence to the algorithm will be recorded on the CRF and will capture instances where the treating clinician overrules the algorithm if they feel it is appropriate to do so. The ultimate responsibility for clinical care of the patient lies with the treating clinician; therefore, the cut-off boundaries for initiation times of antibiotics are not mandatory but are recommended guidance to aid clinical decision-making. The trial aims to assess whether the use of PCT can improve decision-making about which patients receive antibiotics and in what time period. Deviations from the algorithm will not be recorded as protocol violations.

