4.3 ANALYSIS POPULATION

The primary analysis population will include all participants with a completed 'record of consent' form (completed by participants with capacity, a personal consultee if a participant lacks capacity, or a nominated consultee if a personal consultee cannot be identified, or if the participant died prior to obtaining consent) regardless of protocol deviations and adherence, and according to their randomised allocations (intention to treat), with complete data for both co-primary outcomes. A

TPL/008/2(v1.0)

[figure not shown]
Canolfan Ymchwil Treialon

Short title:	ISAP / SAP Template

participant is considered to have complete 28-day mortality data if they have either been confirmed to have died within 28 days or they are known to have been alive at day 28. A sensitivity analysis will be performed including all participants for whom consent has been obtained with complete data for at least one of the co-primary outcomes.

A secondary/sensitivity analysis will estimate the complier average causal effect (CACE) to account for departures from the randomised intervention. For the purposes of this sensitivity analysis, we will define different analysis populations depending on the level of adherence with the PCT-guided algorithm (Figure 3):

- Patients randomised to PCT-guided care in whom a PCT test is done, and a PCT result is available
- Patients randomised to PCT-guided care in whom a PCT test is done, a PCT result is available, and the clinician has seen the PCT result
- Patients randomised to PCT-guided care in whom a PCT test is done, a PCT result is available, the clinician has seen the PCT result and followed the algorithm exactly.

Canolfan Ymchwil Treialon

Short title:	ISAP / SAP Template

Figure 3: Flow diagram defining the different analysis populations in participants randomised to PCT-guided care

We will include a 4 by 4 table comparing the outcomes of the clinical risk assessment and the risk stratification/algorithm (Appendix Table A1).

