It has been recognised that the option to stop the trial early in sequential designs introduces bias to the standard maximum likelihood estimator (MLE) (Cox, 1952). Therefore, we will also calculate unconditional bias-adjusted point estimates. We will derive the bias-adjusted maximum likelihood estimates proposed by Whitehead, by subtracting an estimate of the bias from the MLE (Whitehead, 1986). We will also calculate the uniformly minimum variance unbiased estimator (UMVUE) using the Rao-Blackwell technique. We will calculate the unconditional bias-adjusted point estimates, as we want to determine the point estimates regardless of the stage at which the trial stops. We are interested in the bias as averaged over all possible stopping times, weighted by the respective stage-wise stopping probabilities (Robertson et al., 2023, Grayling & Wason, 2022).

Table 6: Summary of analyses of primary outcomes

Outcome	Analysis	Covariates
	Primary analysis:	Trial arm and baseline NEWS2

Canolfan Ymchwil Treialon

IV antimicrobial	Two-level logistic regression	Trial arm, baseline NEWS2, age,
initiation at 3 hours		number of comorbidities and gender
(superiority)	Secondary analysis:	Trial arm and baseline NEWS2
	Two-level logistic regression with	Trial arm, baseline NEWS2, age,
	bias-adjusted point estimates	number of comorbidities and gender
	Subgroup analyses:	Trial arm, baseline NEWS2, and the
	Two-level logistic regression	organ system of the infection (lower
	(interaction test by model	urinary tract, lower respiratory, intra-
	comparison)	abdominal, bacteraemia, skin, soft
		tissues, etc.)
		Trial arm, baseline NEWS2, and risk
		category based on NEWS2 score at
		baseline (≤4, 5-6 and ≥7)
		Trial arm, baseline NEWS2, and
		managed as suspected COVID-19
		during admission (yes/no)
		Trial arm, baseline NEWS2, and has a
		positive COVID-19 test result +/- 5 days
		from admission (yes/no)
		Trial arm, baseline NEWS2, and PCT
		machine used at the time of
		recruitment (BRAHMS PCT-
		direct/PathFast BRAHMS PCT)
		Trial arm, baseline NEWS2, and
		recruitment date (before 01/12/21,
		between 01/12/21 and 30/11/22, after
		30/11/22)
		Trial arm, baseline NEWS2, and level of
		site ED crowding (upper, middle and
		lower tercile of national monthly
		figures)
	Complier average causal effect	Trial arm, baseline NEWS2, and
	(CACE)	intervention adherence
28-day mortality	Primary analysis:	Trial arm and baseline NEWS2

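### The SAP promises a CACE but names no estimator; the model it attaches does not give one if fitted as written, and the exact-adherence level is doubtful even with an instrumental-variable estimator

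*SAP*

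**What the plan says.** SAP sections 4.3 and 6.2.5 both announce the analysis. In 6.2.5: "A sensitivity analysis will estimate the CACE to account for departures from the randomised intervention". Both sections then turn to groups of patients; in 6.2.5, "we will define different analysis populations depending on the level of adherence to the PCT-guided algorithm (Figure 3", with almost the same sentence in 4.3. The three groups are nested and lie wholly in the PCT arm:

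- Level 1 (result available): "Patients randomised to PCT-guided care in whom a PCT test is done, and a PCT result is available".
- Level 2 (result seen): level 1, and the clinician has also seen the result.
- Level 3 (followed exactly): "the clinician has seen the PCT result and followed the algorithm exactly".

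In Table 6 (section 6.2.1.2), the CACE row of each co-primary outcome has three entries under Covariates: trial arm, baseline NEWS2 and "intervention adherence". In the results shell of Appendix 8.1.1 (the second of two tables numbered A2), a CACE row stands under each co-primary outcome, and each outcome carries a footnote naming multilevel logistic regression. That footnote also gives baseline NEWS2 as the covariate in all models, which does not match Table 6.

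The SAP names no instrument, two-stage model, principal-stratification method or weighting, and no identifying assumption. It does not say how controls are coded for adherence. No title in the reference list of section 7.1 concerns CACE or instrumental variables.

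Section 4.2.1 says what non-adherence is: the CRF "will capture instances where the treating clinician overrules the algorithm if they feel it is appropriate to do so". It also says how the intervention is meant to work: "The trial aims to assess whether the use of PCT can improve decision-making about which patients receive antibiotics".

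**The concern.** A CACE keeps everyone as randomised and uses allocation to recover the effect in those who would receive the intervention if assigned to it. Adherence recorded in the PCT arm cannot do this as an ordinary regressor. It is settled after randomisation by a clinician's view of the patient, and that view is likely to be related to prognosis. If adherence is coded 0 in all controls, the arm term compares PCT-arm non-adherers with all controls, and the adherence term compares adherers with non-adherers inside the PCT arm. Both are open to confounding, and neither is the CACE.

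The second difficulty remains with a correct estimator. At level 3, a patient whose clinician saw the result and overruled the algorithm counts as a non-complier. An instrumental-variable estimate then needs allocation to have had no effect on that patient (the exclusion restriction). Section 4.2.1 describes PCT as an aid to decisions, so a seen result may have altered care without the algorithm being followed exactly.

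At stake is the only planned effect estimate that addresses departures from the randomised intervention. A reader of a non-inferiority trial will look to it when asking whether departures made the arms look alike.

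**Working it through.** The SAP gives no adherence rate and no CACE figure, so there is no figure to reproduce on this point. Two inputs for illustration come from section 3.3: control mortality of 15% and the margin of 2.5 points. As a check on them, 2 x 0.15 x 0.85 x (1.645 + 1.282)^2 / 0.025^2 gives 3,495 per arm, 6,990 in total, against the stated 7,002. All adherence shares, risk ratios and effects below are assumptions.

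**Step 1. Literal model, no true effect in anyone.** Let a be the share adhering and r the ratio of non-adherers' to adherers' risk.

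- Adherers' risk = 0.15 / (a + (1 - a)r). With a = 0.6 and r = 1.5: 0.15 / 1.2 = 12.5%.
- Non-adherers' risk = 1.5 x 12.5% = 18.75%.
- Arm term = 18.75 - 15 = **+3.75 points**.
- Adherence term = 12.5 - 18.75 = **-6.25 points**.
- Instrumental-variable (Wald) estimate = (PCT-arm risk - control risk) / a = (0.6 x 12.5 + 0.4 x 18.75 - 15) / 0.6 = (15 - 15) / 0.6 = **0**, the true value.

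Before NEWS2 and site are added, arm and adherence form only three cells. A logistic model reproduces the same three risks, so the result does not depend on the linear scale. A simulation with 7,002 patients and 300 runs gave means of +3.7, -6.3 and, for the Wald estimate, -0.1 points (SD across runs 1.4).

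**Step 2. Range.** For a from 40% to 80% and r from 1.25 to 2.0, the arm term runs from +1.3 to +10.0 points and the adherence term from -3.3 to -12.5. With r below 1 (adherers sicker), both signs reverse.

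**Step 3. Level 3 with a correct instrumental-variable estimator.** Assume 95% have a result available and a share f of these are followed exactly. The true effect is -10 points in followers and -5 points in overruled patients, and none without a result.

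- f = 0.5: ITT effect = 0.95 x (0.5 x -10 + 0.5 x -5) = -7.125. Dividing by 0.95 x 0.5 = 0.475 gives **-15.0** against a true -10.
- f = 0.3: -6.175 / 0.285 = **-21.7**.
- f = 0.7: -8.075 / 0.665 = **-12.1**.
- No effect in overruled patients: -10 at every f, so no bias.

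In general the bias is (1 - f)/f times the effect in overruled patients. At level 1 with f = 0.5, the estimator gives -7.125 / 0.95 = -7.5, the average effect over all patients with a result, as it should.

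**Step 4. What a correct CACE does to a bound.** It divides by the share receiving. Treating that share as known, an illustrative ITT upper bound of 1.6 points becomes 1.6 / 0.60 = 2.7 at 60% receipt, and 1.6 / 0.95 = 1.7 at 95%. Against a margin of 2.5, it matters only if receipt is well below complete.

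**The case against.** The strongest reply is that the target is stated and the pieces fit it. The Covariates column of Table 6 always includes trial arm, so it is not a list of adjusters only; arm, NEWS2 and adherence could be the instrument, covariate and treatment received of an instrumental-variable model. The CACE rows do not name logistic regression, although other rows do. The shell footnote is loose, since it also conflicts with the rows adjusted for more covariates. The three groups can be read as alternative definitions of a complier, and non-compliance in one arm only is a standard CACE setting. All of this stands as a possible reading. It does not supply the estimator, and the only model the SAP attaches to the CACE rows is ordinary regression.

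A reader might infer that the SAP plans a per-protocol comparison of adherers with all controls. The documents do not support that. No section excludes non-adherers, the adherence shell has yes, no and missing rows, and in a sample of adherers plus controls adherence would equal arm, so the two could not enter one model. A reader might also infer that no instrumental-variable estimate is possible, or that the bias favours PCT. The first is too strong: levels 1 and 2 are more plausible, though not certain in an open-label trial, and level 3 fails only if overruled patients were affected. The second needs overruling to fall mainly on sicker patients, which the SAP does not say.

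It is also fair that section 4.2.1 makes clinician discretion part of the strategy. Intention to treat then estimates the strategy as designed, and the CACE is supplementary. Adjustment for NEWS2 would remove some of the confounding.

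**Conclusion.** The point holds in two parts. First, the CACE has no stated estimator, control coding or assumptions, and the model attached to it does not estimate a CACE if fitted as written. In the worked null case the two terms are +3.75 and -6.25 points where the truth is 0. Second, at the exact-adherence level the exclusion restriction is doubtful. An instrumental-variable estimate there is biased whenever overruled patients are affected: -15.0 against -10 with half followed and half the effect in the overruled.

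These sizes rest on assumed adherence, risk and effect values; both magnitude and direction could differ in the trial. The finding concerns a sensitivity analysis. The decision on effectiveness rests on the intention-to-treat co-primary analyses and is not touched.

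**What to change.** In sections 4.3 and 6.2.5, replace the description of adherence populations with a named analysis:

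- Keep all participants of the primary analysis population as randomised.
- Estimate the CACE on the risk-difference scale, with randomised arm as instrument, receipt as exposure (controls coded as not receiving), and NEWS2 and site as exogenous covariates.
- Use the confidence level of the primary analysis for each outcome, and state the identifying assumptions.
- Report it for result available and for result seen.
- Label the exact-adherence level descriptive or exploratory, and say that the exclusion restriction is doubtful there.

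In Table 6, remove adherence as an ordinary covariate from both CACE rows. In the Appendix 8.1.1 shell, give the CACE rows their own method footnote and correct the covariate statement. The deviation log shows that analyses have already been run but does not mention the CACE. If the literal model was fitted, re-run the analysis and record this in the log; otherwise record the estimator that was used.

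The cost is wording, a standard instrumental-variable command in Stata and possibly one re-run; no new data are needed. The price is that the trial would no longer offer a causal estimate for exact adherence to the algorithm, the only level that captures overruling.

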6.2.6 SUBGROUP ANALYSES

We will conduct seven separate subgroup analyses, stratified by:

- The organ system of the infection (initial working diagnosis):
 - Upper respiratory tract infection
 - Skin/soft tissue infection
 - Urinary tract infection/urosepsis
 - Central nervous system infection
 - Gastrointestinal tract/abdominal infection
 - Bone/joint/muscle infection
 - Lower respiratory tract infection/community-acquired pneumonia
 - Sepsis (unknown source)
 - Other infections
 - Not infection
- Risk category based on NEWS2 score at baseline:
 - ≤4
 - 5-6
 - ≥7
- Managed as suspected COVID-19 during admission:
 - Yes
 - No
- Positive COVID-19 test result +/- 5 days from admission:
 - Yes
 - No
- PCT machine used at time of recruitment:
 - BRAHMS PCT-direct

TPL/008/2(v1.0)

Canolfan Ymchwil Treialon

Short title: ISAP / SAP Template

- PathFast BRAHMS PCT
- Recruitment date:
 - Before 1st December 2021
 - Between 1st December 2021 and 30th November 2022
 - After 30th November 2022
- Level of site ED crowding (percentage of patients who spent >12 hours from decision to admit to admission) at time of randomisation:
 - Upper tercile of national monthly figures
 - Middle tercile of national monthly figures
 - Bottom tercile of national monthly figures

We will investigate whether the treatment effect varies between subgroups by including the subgroup variable as a covariate in the main analysis model, both with and without a treatment-arm interaction term. The models with and without the interaction term will be compared using a likelihood-ratio test (LRT). We will report the LRT χ^2 statistic and illustrate the direction of the subgroup effect using forest or interaction plots.

We will also assess whether adherence to the intervention varies according to levels of ED crowding at the time of randomisation. We will conduct a two-level logistic regression (patients nested within sites) with algorithm adherence (yes/no) as the outcome variable and the level of ED crowding as the explanatory variable, controlling for baseline NEWS2 score (minimisation variable). NHS England publishes monthly A&E attendances and emergency admissions data. We will calculate the percentage of emergency admission patients who spent >12 hours from decision to admit to admission per month per site and compare these to the national monthly figures. We will rerun the co-primary analyses for subgroups of the least, middle, and most crowded EDs. As an exploratory analysis we may include ED crowding as an additional covariate and include time varying interaction terms. If the data allows, we may also explore the effect of daily ED crowding levels on the co-primary outcomes for a subgroup of sites.

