3. STUDY MATERIALS

3.1 TRIAL DESIGN

Parallel, two-arm, open-label, individually randomised controlled trial with two co-primary endpoints, an internal pilot phase, and group-sequential stopping rules for effectiveness. Participants are randomised in a ratio of 1:1 to PCT-guided assessment added to NEWS2 and local standard care, or NEWS2 and local standard care alone. The participant flow diagram (Figure 1) provides further details.

Canolfan Ymchwil Treialon

[figure not shown]

Figure 1: PRONTO trial participant flow diagram.

TPL/008/2(v1.0)

Short title:

ISAP / SAP Template

Canolfan Ymchwil Treialon

Short title: ISAP / SAP Template

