5. STUDY POPULATION

5.1 SCREENING DATA

Patients with suspected sepsis will be identified at ED triage. After initial NEWS2 and assessment according to the current standard of care the eligibility criteria will be assessed and if no exclusion criteria apply, patients will be enrolled into the trial and randomised. A screening log of all eligible and randomised patients will be kept at each site so that any biases from differential recruitment will be detected. Tables will present the following summaries (overall and by study site): the number of days recruiting, number of patients screened, number of patients recruited, number of patients recruited per day, number of screened patients not recruited, and the reason for non-recruitment.

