5.4 TIERED CONSENT PROCESS

Due to time constraints in managing suspected sepsis, patients will be randomised into either the standard care arm or interventional arm on diagnosis with suspected sepsis prior to consent being obtained. The participant will be approached within 72 hours of randomisation to complete the formal informed consent process. The process is described in the participant consent flowchart (PRONTO Protocol Version 3.1 dated 23/10/23; Section 9.3; Figure 2). During this process participants can consent to different aspects of the trial using a tiered consent approach.

Participants can agree to the following aspects of the study:

- 1. Information collected as part of the trial and data from medical records from the date of randomisation up to the date of consent can be used in the trial.
- 2. Data from medical records can be collected from the date of randomisation to 90 days after this date.
- 3. Participant to be contacted by research staff at day 28 and day 90 to ask about health, wellbeing and any further medical treatment they may have received.

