5.6 BASELINE PARTICPANT CHARACTERISTICS

- 5.6.1 LIST OF BASELINE DATA
 - Age
 - Gender
 - Ethnicity
 - Timing of initial assessments and ED admission
 - Duration of symptoms
 - Initial diagnosis
 - Initial treatment
 - History of oral antibiotic use in 14 days prior to admission
 - Comorbidities (Charlson Comorbidity Index)
 - COVID-19 status
 - C-reactive protein (CRP) at baseline

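### The subgroup of patients managed as suspected COVID-19 is fixed after randomisation and can depend on the PCT result, so its interaction tests can be biased; the positive-test subgroup shares the problem more weakly.

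*SAP*

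**What the plan says.** Section 6.2.6 of the SAP lists seven subgroup analyses. Two concern COVID-19: "Managed as suspected COVID-19 during admission" and "Positive COVID-19 test result +/- 5 days from admission", each coded yes or no. Both are repeated in Table 6 (the first with the wording "during admission (yes/no") and in Table A4, for each co-primary outcome. The subgroup variable is added to the main model, and models with and without an arm interaction are compared by likelihood-ratio test.

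Other entries in the same list have a time anchor. One reads "Risk category based on NEWS2 score at baseline"; PCT machine is taken at recruitment and ED crowding at randomisation. Neither COVID-19 variable is limited to what was known before randomisation.

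On timing, section 5.1 states "Patients with suspected sepsis will be identified at ED triage", and section 5.4 says patients are "randomised into either the standard care arm or interventional arm on diagnosis with suspected sepsis prior to consent being obtained". Section 3.1 describes the trial as "Parallel, two-arm, open-label, individually randomised controlled trial". Section 2.1 presents PCT as an aid to identifying bacterial infection, and section 4.3 makes the clinician's sight of the result one of its adherence levels.

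Two other places bear on COVID-19. Section 5.6.1 lists "COVID-19 status" among baseline data, without a window or definition. Table 2 lists COVID diagnosis, with its date, among outcome data collected up to day 28.

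**The concern.** A subgroup comparison keeps the protection of randomisation only if membership cannot be changed by the allocated arm. Here it can. A clinician who sees a low PCT result in a febrile patient has a reason to move towards a viral working diagnosis; one who sees a high result has a reason to move away from it. The control clinician has no such prompt. Patients labelled *yes* in the two arms may then differ in case mix, and so may those labelled *no*. The model conditions on that label, and the interaction term mixes treatment effect with case-mix shift.

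The antibiotic outcome has a further difficulty. It is assessed within 3 hours of ED admission (section 6.1.2), whereas the management label can be set later in the stay. The label may follow the outcome, and may partly reflect the same clinical thinking that decided it.

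A COVID-19 interaction for mortality could be read as showing in whom PCT-guided care is safe or unsafe. As defined, such a finding could be an artefact.

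**Working it through.** **Timing.** The SAP gives no figure on this point, so there is none to reproduce. The sequence follows from the sections cited above:

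1. Randomisation takes place in the ED, on diagnosis of suspected sepsis.
2. The PCT result becomes available to the intervention clinician.
3. The 3-hour antibiotic outcome is settled.
4. The management label stays open until the admission ends, and the test window until day 5 after admission.

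Both labels can be completed after steps 2 and 3.

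**Illustration for mortality.** From the SAP: 7002 patients, so 3501 per arm (section 3.3). Everything else is an assumption. There are two latent patient types and no treatment effect on death in anyone; the arm changes only who receives the label.

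Let type 1 have prevalence π. Type mortalities are m₁ and m₀, and label probabilities a (type 1) and b (type 0). Then:

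- Fraction labelled yes: p = πa + (1−π)b
- Mortality in yes: [πa·m₁ + (1−π)b·m₀] / p
- Mortality in no: [π(1−a)m₁ + (1−π)(1−b)m₀] / (1−p)
- Rejection rate: 1-df test at 5%, noncentrality (ln ROR)² / V. ROR is the ratio of the yes and no odds ratios. V sums 1/[n·f·m(1−m)] over the four arm-by-label cells, where n = 3501, f is the fraction of the arm in the cell and m its mortality. This is a single-level approximation without covariates.

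*Set A: PCT only adds labels among non-cases.* π = 0.15 true COVID-19, m₁ = 0.20, m₀ = 0.12, a = 0.95 in both arms; b = 0.25 in control, 0.30 or 0.35 in the PCT arm.

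- Control: p = 0.1425 + 0.2125 = 0.355; mortality in yes = (0.0285 + 0.0255)/0.355 = 15.21%.
- PCT, b = 0.30: p = 0.3975; (0.0285 + 0.0306)/0.3975 = 14.87%. Difference −0.34 points; ROR 0.97; rejection 5.4%.
- PCT, b = 0.35: p = 0.44; (0.0285 + 0.0357)/0.44 = 14.59%. Difference −0.62 points; ROR 0.95; rejection 6.4%.

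The standard error of the yes-stratum difference is about 1.4 points, so these shifts are about 0.25 and 0.46 of a standard error.

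*Set B: PCT can move labels both ways.* π = 0.30 low-PCT patients, m₁ = 0.08, m₀ = 0.18 (overall 0.024 + 0.126 = 15%, the control rate assumed in section 3.3); control a = 0.30, b = 0.15.

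- Control: p = 0.09 + 0.105 = 0.195; mortality in yes = (0.0072 + 0.0189)/0.195 = 13.38%; in no = (0.0168 + 0.1071)/0.805 = 15.39%.
- Example, +5/−5: p = 0.105 + 0.07 = 0.175; mortality in yes = (0.0084 + 0.0126)/0.175 = 12.00%.

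| Label shift in PCT arm, points (low-PCT / high-PCT) | Difference in yes, points | Difference in no, points | ROR | Rejection rate |
|---|---|---|---|---|
| 0 / 0 | 0.0 | 0.0 | 1.00 | 5% |
| +5 / 0 | −0.4 | +0.1 | 0.96 | 6% |
| +5 / −5 | −1.4 | +0.2 | 0.87 | 12% |
| +10 / −5 | −1.7 | +0.4 | 0.83 | 18% |
| +10 / −10 | −3.1 | +0.5 | 0.71 | 41% |

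The first row is what a label fixed before randomisation guarantees on average. No calculation was made for the antibiotic outcome or for the positive-test subgroup; for those the argument rests on timing alone.

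**The case against.** The strongest reply is that the bias may be trivial. Set A and the +5/0 row of Set B, where PCT only adds labels in one patient type, barely move the test: 5.4% to 6.4%. The larger rates need PCT to raise the label in one type and lower it in the other, and no input on labelling comes from the SAP. This stands: the route to bias is shown, its size is not.

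The two subgroups are also not equally exposed. A positive test close to admission is mostly a marker of infection present on arrival. PCT does not change viral presence, and part of the window precedes randomisation. Bias would need testing or retesting that depends on arm, infection acquired after admission, or death or discharge before a test. The SAP does not say whether testing was routine. This stands too, and makes the second subgroup the weaker case.

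A reader might infer that the SAP contradicts itself by listing COVID-19 status as baseline data. It does not show that. The variable is undefined: it may be pre-randomisation status, or it may be the same data as the subgroup labels. A reader might also measure the spurious differences against the 2.5-point non-inferiority margin. The SAP applies that margin to the overall mortality comparison and to no subgroup, so it is not a fair yardstick here.

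Finally, a strict pre-randomisation rule would class as negative some patients swabbed shortly afterwards. That is a real cost.

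**Conclusion.** The point holds in a limited form. The management-label subgroup can be influenced by the arm, and nothing in the SAP guards against it: there is no caveat, pre-randomisation version or sensitivity analysis for it. Its interaction tests and stratum estimates can therefore be biased for both co-primary outcomes. The positive-test subgroup has the same timing flaw to a lesser degree.

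Size and direction cannot be determined from the SAP. The mortality illustration runs from negligible to serious and rests on assumed prevalence, mortality and labelling.

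It would be wrong to infer that the trial's main conclusions are in doubt. The co-primary models do not contain these variables, and effectiveness is judged by Tables 3 and 5, which use no subgroup. The matter concerns two of seven subgroup analyses and is worth correcting because the correction is cheap.

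**What to change.** In section 6.2.6, Table 6 and Table A4, define the COVID-19 subgroup used for the interaction test from information dated on or before randomisation. Candidates are the COVID-19 status in section 5.6.1, once its content and timing have been checked, or a diagnosis or test with a date; Table 2 already records the date of COVID diagnosis.

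Keep the two current definitions as exploratory. Report label frequency by arm for each, and state that membership can be settled after randomisation and, for the antibiotic outcome, after the outcome itself.

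The deviation log dates post-hoc analyses from 24/06/24, so the planned subgroup analyses may already have been run. In that case, enter the redefinition in the log as a deviation, made after results were known if that is so.

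The cost is a change of wording, a check of what the baseline variable holds, and a rerun of the affected models. The price is a smaller COVID-positive group, hence lower precision, and some misclassification of patients tested soon after randomisation. If no pre-randomisation variable proves usable, the label frequencies and the caveat are the minimum.
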